8.1.2. Reporting

Adverse events that begin or worsen after informed consent should be recorded on the Adverse Events form of the eCRF. Conditions that were already present at the time of informed consent should be recorded on the Medical History form in the eCRF. Monitoring for the occurrence of new AEs should be continued for at least 60 days after the last dose of study drug or until the start of new anticancer therapy, whichever occurs first. Adverse events (including laboratory abnormalities that constitute AEs) should be described using a diagnosis whenever possible rather than by individual underlying signs and symptoms.

The term "disease progression" should be recorded as an AE/SAE only if there are no other identifiable AEs/SAEs associated with the disease progression at the time of reporting. For events associated with disease progression, the relevant signs and symptoms should be reported using a diagnosis whenever possible rather than individual underlying signs and symptoms. When a clear diagnosis cannot be identified, each sign or symptom should be reported as a separate AE. If the events resulting from disease progression meet the criteria for an SAE (eg, resulted in hospitalization, a life-threatening event, or death), the specific event(s) should be reported as an SAE(s) as described in [Section 8.3.2](#). In both cases (ie, AEs or SAEs related to disease progression), it should be indicated that each event (reported as a diagnosis or as signs and symptoms) is related to disease progression on the Adverse Events form of the eCRF.

The severity of AEs will be assessed using CTCAE v4.03 Grades 1 through 4. The CTCAE v4.03 severity of Grade 5 will not be used; AEs resulting in death will be graded accordingly using Grades 1 through 4 and have the outcome noted as fatal. If an event is not classified by CTCAE, the severity of the AE will be graded according to the scale below to estimate the grade of severity:

Grade 1	Mild; asymptomatic or mild symptoms; clinical or diagnostic observations only; intervention not indicated.
Grade 2	Moderate; minimal, local, or noninvasive intervention indicated; limiting age-appropriate activities of daily living.
Grade 3	Severe or medically significant but not immediately life-threatening; hospitalization or prolongation of hospitalization indicated; disabling; limiting self-care activities of daily living.
Grade 4	Life-threatening consequences; urgent intervention indicated.

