4.1.4. Handling of Missing and Incomplete Data

In general, values for missing data will not be imputed unless methods for handling missing data are specified in this section or relevant sections.

Partial disease/cancer diagnosis date will be handled as follows:

- If only the day is missing, then the imputed day will be the first of the month.
- If both the month and day are missing, then the imputed day and month will be 01 JAN.
- No imputation will be done if the date is completely missing.

Missing or partial date of last dose will be handled as follows:

- If only the day is missing, then the imputed date of the last dose will be the earlier date of the first day of the month or the date that the subject discontinued treatment.
- Otherwise, the date that the subject discontinued treatment will be used as the date of the last dose.

For relevant efficacy endpoints, partial death date will be imputed as follows:

- If mmYYYY for the last contact date = mmYYYY for the death date, then the death date will be set to the day after the last contact date.
- If mmYYYY for the last contact date < mmYYYY for the death date, then the death date will be set to the first day of the death month.
- Otherwise, the partial death date will not be imputed.

For prior and concomitant medications:

The start/stop dates recorded in the CRF by the investigator and his or her research staff will be used to identify when a concomitant medication was taken during the study. Any missing start date must be queried for resolution. Unresolved missing start dates will be handled as follows:

- If the date is completely missing, the medication will be considered both prior and concomitant.
- If only the day is missing, and the last day of the month is before the first dose date on Day 1, then the concomitant medication will be considered as starting before Day 1, and the incomplete date will be imputed as the last day of the month.
- If only the day is missing, and the first day of the month is after the first dose date on Day 1, then the concomitant medication will be considered as starting after Day 1, and the incomplete date will be imputed as the first day of the month.
- If only the day is missing, and the month is equal to the month of the first dose date on Day 1, then the incomplete date will be imputed as the first day of the month.

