4.1.5. Cycle Length and Duration

Cycle 1 Day 1 is the day that the first dose of study drug is administered. Scheduled cycle length is 14 days. Actual Day 1 of subsequent cycles will correspond with the first day of administration of INCAGN01949 in that cycle; thus, treatment cycles may become out of sync with the originally planned schedule and cycle length may be different from 14 days. The date of the Day 1 of subsequent cycles recorded on CRF will be used as the Day 1 of the subsequent cycles.

Note that there leaves flexibility to test different dosing schedules of INCAGN01949 based on evolving PK [REDACTED] data. The SAP does not specify all of the dosing schedule possibilities.

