8.1. General Considerations

Summary tables may be replaced with listings when appropriate. For instance, an AE frequency table may be replaced with a listing if it only contains a few unique PTs reported on relatively few subjects. Data from the Part 1 portion will be summarized separately where appropriate. Additional summaries for specific subgroups may be included on an ad hoc basis.

Unless otherwise stated, table summaries will be limited to AEs occurring within 60 days of the last administration of study drug.

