8.2. Adverse Events

8.2.1. Adverse Event Definitions

A TEAE is any AE either reported for the first time or worsening of a pre-existing event after first dose of study drug. Analysis of AEs (as discussed below) will be limited to TEAEs, but data listings will include all AEs regardless of their timing in relation to study drug administration.

Adverse events will be tabulated by MedDRA PT and SOC. Severity of AEs will be graded using the NCI CTCAE. The CTCAE version 4.03 is used for this study. The CTCAE reporting guidelines and grading details are available on the Cancer Therapy Evaluation Program website.

The subset of AEs considered by the investigator to be related to study drug will be considered to be treatment-related AEs. If the investigator does not specify the relationship of the AE to study drug, the AE will be considered to be treatment-related. The incidence of AEs and treatment-related AEs will be tabulated. In addition, SAEs will also be tabulated.

A grading (severity) scale is provided for each AE term. If the toxicity is not included in the CTCAE v4.03 criteria, it will be rated on a scale of 1 to 4 as follows: 1 = mild, 2 = moderate, 3 = severe, and 4 = life threatening. All toxicities will be graded based on the worst level reached, not the level they may have reached if they had not been treated. When the intensity of an AE changes over time for a reporting period (eg, between visits), each change in intensity will be collected as an AE until the event resolves. Only the worst grade will be reported in AE summaries. Also, the Grade 3 or higher AEs will be reported in a listing.

Any missing onset date, causality, or severity must be queried for resolution. Unresolved missing causality and severity will be handled according to the following rules:

- An unresolved missing causality will be considered treatment-related.
- An unresolved missing severity will be identified as an unknown severity.

For purposes of analysis, all AEs will be considered TEAEs unless the AE can unequivocally be defined as not treatment-emergent.

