	Average Dose (mg)	xxx	x.xxxxx	x.xxxxxx	x.xxx	x.xxxxx	x.xxxx
	Average Dose (mg/kg)	xxx	x.xxxxx	x.xxxxxx	x.xxx	x.xxxxx	x.xxxx

FOLDER\PROGRAM\OUTPUT: XXXXXX\XXXXXX.SAS\XXXXXX.LST

DATE (TIME): MMDDYYYY (hh:mm)

- [a] Duration of treatment (days) = Date of last dose - Date of first dose + 1.
- [b] Average dose (mg/kg) = [total actual dose taken (mg/kg) by the subject]/[number of cycles with a nonzero dose]
- [c] Average dose (mg) = [total actual dose taken by each subject (mg) in a cycle]/[number of subjects with a nonzero dose in that cycle]

Abbreviations: Min = minimum; Max = maximum; STD = standard deviation;

Reference: Listings 2.6.1

PROTOCOL: INCAGN 1949-101
DRUG/INDICATION: OX40/Advanced or Metastatic Solid Tumors
TLF VERSION: Draft

(Page n of N)
DATABASE VERSION: XXXXX

Table 3.1.1.2
Summary of Study Drug Exposure
(Population: Part 2 FAS Population)

Cancer Type (mg/kg)	Variable	Descriptive Summary				
		N	Mean	STD	Min	Median
Endometrial	Number of Treatment Cycles	xxx	x.xxxx	x.xxxxxx	x.***	x.xxxx
	Duration of Treatment (Days)	xxx	x.xxxx	x.xxxxxx	x.***	x.xxxx
	Average Dose (mg)	xxx	x.xxxx	x.xxxxxx	x.***	x.xxxx
	Average Dose (mg/kg)	xxx	x.xxxx	x.xxxxxx	x.***	x.xxxx
Melanoma	Number of Treatment Cycles	xxx	x.xxxx	x.xxxxxx	x.***	x.xxxx
	Duration of Treatment (Days)	xxx	x.xxxx	x.xxxxxx	x.***	x.xxxx
	Average Dose (mg)	xxx	x.xxxx	x.xxxxxx	x.***	x.xxxx
	Average Dose (mg/kg)	xxx	x.xxxx	x.xxxxxx	x.***	x.xxxx
NSCLC	Number of Treatment Cycles	xxx	x.xxxx	x.xxxxxx	x.***	x.xxxx
	Duration of Treatment (Days)	xxx	x.xxxx	x.xxxxxx	x.***	x.xxxx
	Average Dose (mg)	xxx	x.xxxx	x.xxxxxx	x.***	x.xxxx
	Average Dose (mg/kg)	xxx	x.xxxx	x.xxxxxx	x.***	x.xxxx
Ovarian	Number of Treatment Cycles	xxx	x.xxxx	x.xxxxxx	x.***	x.xxxx
	Duration of Treatment (Days)	xxx	x.xxxx	x.xxxxxx	x.***	x.xxxx
	Average Dose (mg)	xxx	x.xxxx	x.xxxxxx	x.***	x.xxxx
	Average Dose (mg/kg)	xxx	x.xxxx	x.xxxxxx	x.***	x.xxxx
RCC	Number of Treatment Cycles	xxx	x.xxxx	x.xxxxxx	x.***	x.xxxx
	Duration of Treatment (Days)	xxx	x.xxxx	x.xxxxxx	x.***	x.xxxx
	Average Dose (mg)	xxx	x.xxxx	x.xxxxxx	x.***	x.xxxx
	Average Dose (mg/kg)	xxx	x.xxxx	x.xxxxxx	x.***	x.xxxx

FOLDER\PROGRAM\OUTPUT: XXXXXX\XXXXXX.SAS\XXXXXX.LST

DATE (TIME): MMDDYYYY (hh:mm)

- [a] Duration of treatment (days) = Date of last dose - Date of first dose + 1.
- [b] Average dose (mg/kg) = [total actual dose taken (mg/kg) by the subject]/[number of cycles with a nonzero dose]

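### SAP 4.1.4 sets a last-dose date with a missing day to the first of the month, which can precede recorded infusions and, if it sets the 60-day AE window, shortens it by up to 30 days

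*SAP*

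**What the plan says.** SAP 4.1.4 (Handling of Missing and Incomplete Data) has two rules for the date of last dose. If only the day is missing, the date becomes "the earlier date of the first day of the month or the date that the subject discontinued treatment". In every other case of a missing or partial date, "Otherwise, the date that the subject discontinued treatment will be used as the date of the last dose". Neither rule has a floor at the first dose or at the latest recorded infusion.

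The date of last dose has two uses that bear on this point:

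- **AE tables.** SAP 8.1 states, with an allowance for exceptions, that "table summaries will be limited to AEs occurring within 60 days of the last administration of study drug". Protocol 8.1.2 collects to a matching horizon: "Monitoring for the occurrence of new AEs should be continued for at least 60 days after the last dose of study drug", or until new anticancer therapy starts if that is sooner.
- **Treatment duration.** The footnote to the exposure shells (Tables 3.1.1.1 and 3.1.1.2, SAP Appendix A) gives "Duration of treatment (days) = Date of last dose - Date of first dose + 1".

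On dosing, SAP 4.1.5 says "Scheduled cycle length is 14 days" and that "The date of the Day 1 of subsequent cycles recorded on CRF will be used as the Day 1 of the subsequent cycles". Infusion dates are therefore available to the imputation, which does not use them. SAP 8.2.1 adds that "data listings will include all AEs regardless of their timing in relation to study drug administration".

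**The concern.** The rule compares two dates of which one can never be the earlier. A comparison with the discontinuation date would do some work if the other candidate were the last day of the month. With the first day, it does none.

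The two rules also pull in opposite directions. When the month is known, the last dose moves back to the earliest possible day. When less is known, it moves forward to the discontinuation date.

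The early date matters in two ways. It can contradict the subject's own dosing record. If it also anchors the 60-day window, it shortens post-treatment follow-up in the AE tables, and AEs are the primary endpoint. Protocol 5.4.7 warns that immune-related AEs can appear well after the last dose, so the late part of the window is not empty by design. The SAP's other safety defaults lean towards inclusion: in 8.2.1, unresolved missing causality counts as related, and AEs count as treatment-emergent unless clearly not. This rule leans the other way.

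**Working it through.** The plan gives no figure to reproduce, so the check is calendar arithmetic.

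**Notation.** D is the true date of last dose, F the first day of that month, L the last day of that month, and S the date treatment was discontinued. The rule imputes min(F, S).

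**1. What the rule returns.** D is on or after F by definition, and S is on or after D because treatment cannot stop before its last dose. So S is on or after F, and min(F, S) = F always. As a check, 365 last-dose dates were each combined with 60 gaps from last dose to discontinuation (0 to 59 days). In none of the 365 × 60 = 21,900 combinations did the rule return a date other than F.

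**2. Against recorded infusions.** Take D = 31 August on 14-day cycles, with earlier infusions on 17 and 3 August. The imputed date is 1 August, before both. In general, the imputed date precedes the previous infusion when the day of the month minus 14 exceeds 1, that is, from day 16 on. Over a non-leap year:

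- 14-day dosing: 7 × 16 + 4 × 15 + 13 = 185 of 365 dates (50.7%).
- 21-day dosing (day 23 on): 7 × 9 + 4 × 8 + 6 = 101 of 365 dates (27.7%).

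These shares assume a uniform day and a subject with at least one earlier infusion.

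**3. Treatment duration.** First dose 10 August, last dose 24 August:

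- True: 24 - 10 + 1 = 15 days.
- Imputed: 1 - 10 + 1 = -8 days.

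**4. The 60-day window, if the imputed date anchors it.** The backward shift is D - F = day of month - 1.

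| Month length | Largest shift (days) | Days of true window left |
|---|---|---|
| 31 | 30 | 30 |
| 30 | 29 | 31 |
| 29 | 28 | 32 |
| 28 | 27 | 33 |

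For D = 31 August, the window should end on 30 October (31 August + 60). It would end on 30 September (1 August + 60). AEs starting on days 31 to 60 after the true last dose would leave the tables.

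If the day is uniform over a non-leap year, the mean shift is (7 × 31 × 15 + 4 × 30 × 14.5 + 28 × 13.5) / 365 = (3255 + 1740 + 378) / 365 = 5373 / 365 = 14.7 days. The date moves by at least one day for 353 of 365 dates (96.7%).

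**5. The alternative min(L, S).** Both L and S are on or after D, so the imputed date is never too early and the window is never shortened. With S set 0, 7, 14 or 28 days after D, the forward shift ran from 0 to 28 days. The ceiling is 30 days: a dose on the 1st of a 31-day month, with discontinuation at least 30 days later.

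**The case against.** The strongest case is that this fallback will almost never be used. Study drug is infused at the site, and receipt is documented by staff and monitored (Protocol 5.3). The IRT is contacted when drug is ordered for each cycle (Protocol 5.1.1), the date of last dose is entered in the eCRF at withdrawal (Protocol 5.5.2), and each cycle's Day 1 is on the CRF. The documents give no rate of missing days. All of this stands, and it makes the expected effect on any table close to nil.

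Second, the link to the AE window is an inference. SAP 8.1 speaks of the last administration, does not cite 4.1.4, and allows exceptions. That stands too, so the point about the window has to be conditional. The inference is still reasonable, because 4.1.4 is the only rule that supplies a date when the last dose is partial.

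Third, the harm is contained. Listings keep all AEs, with separate ones planned for serious, Grade 3 or higher, fatal, treatment-related and immune-related events. At least 30 days of the true window survive. Monitoring for new AEs may end sooner if new anticancer therapy starts. Dose-escalation decisions rest on events through study Day 28 (Protocol 5.4.2) and do not use this date. The exposure measures in SAP 6.4 do not use it either.

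Fourth, an early date avoids overstating exposure, and 4.1.4 also uses the first of the month for diagnosis dates and some death dates. That is a fair account of possible intent, and it means that inverted wording cannot be taken as proven. It does not explain the redundant comparison or excuse a date that precedes a recorded infusion.

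The default in SAP 8.2.1 that AEs count as treatment-emergent does not rescue late events. It concerns onset or worsening after the first dose and leaves the 60-day limit in place.

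**Conclusion.** The rule is wrong as written, and the point is minor. Followed literally, it always gives the first of the month. It can contradict infusion dates on the CRF and can produce a negative treatment duration. Those results need only one assumption, that discontinuation is not recorded before the last dose.

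The effect on AE tables is conditional. If the imputed date sets the window in SAP 8.1, an affected subject loses up to 30 of 60 post-dose days, or about 15 on average under a uniform day. Few if any subjects should be affected.

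A reader might infer that related AEs will be lost from the safety report, or that half the safety data are at risk. The documents support neither. The 50% is the worst case (a dose on the 31st) for one subject's post-treatment window. It is not a share of that subject's AEs or of the primary endpoint. An excluded event would leave a summary table but stay in the listings.

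**What to change.** Reword the first rule in SAP 4.1.4: when only the day is missing, impute the earlier of the last day of that month and the date treatment was discontinued, and never a date before the latest fully recorded infusion. With consistent data the first part already satisfies the floor. The floor guards against a discontinuation date entered too early. It would also help to state in SAP 8.1 whether an imputed last-dose date defines the 60-day window.

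The change is one line and uses dates already collected. Its cost is error in the other direction. The last dose may be placed up to about four weeks late (28 days in the cases enumerated, 30 at most). That slightly lengthens treatment duration and admits some AEs more than 60 days after the true last dose. For safety tables this is the conservative direction.

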4.1.5. Cycle Length and Duration

Cycle 1 Day 1 is the day that the first dose of study drug is administered. Scheduled cycle length is 14 days. Actual Day 1 of subsequent cycles will correspond with the first day of administration of INCAGN01949 in that cycle; thus, treatment cycles may become out of sync with the originally planned schedule and cycle length may be different from 14 days. The date of the Day 1 of subsequent cycles recorded on CRF will be used as the Day 1 of the subsequent cycles.

Note that there leaves flexibility to test different dosing schedules of INCAGN01949 based on evolving PK [REDACTED] data. The SAP does not specify all of the dosing schedule possibilities.

4.2. Variable Definitions

4.2.1. Derived Variables

The following variable is provided on the CRF but also derived for analysis purposes. The MSKCC ([Motzer et al 2004](#)) criteria will be summarized for both investigator reported and derived data for RCC subjects.

4.2.1.1. MSKCC Criteria for Renal Cell Carcinoma Subjects

The MSKCC ([Motzer et al 2004](#)) score will be derived as a prognostic tool for RCC subjects enrolled in Parts 1 and 2. The calculation for the MSKCC score is provided below as the sum of 5 component "no" vs "yes" (0 vs 1) scores. For each component, subjects will have a score of 1 for each criterion they meet. An MSKCC total score of 0 indicates a prognosis of Good. A MSKCC total score of 1 to 2 indicates an Intermediate prognosis, and a total score of ≥ 3 indicates a Poor prognosis. The derivation of MSKCC will use screening data; if screening data is not available, then Cycle 1 Day 1 data will be used.

1. Time from diagnosis to systematic treatment < 1 year
2. Low hemoglobin
 - Men (normal): 13.5 to 17.5 g/dL
 - Women (normal): 12.0 to 15.5 g/dL
3. Calcium > 10 mg/dL (> 2.5 mmol/L)
4. Lactate dehydrogenase > 420 U/L
5. Performance status: Karnofsky < 80% or ECOG > 1

Missing dates for time of first systemic treatment will be handled according to rules for missing partial disease/cancer diagnosis date that are given in [Section 4.1.4](#).

4.2.1.2. Prior and Concomitant Medication

Prior medication is defined as any nonstudy medication started before the first dose of INCAGN01949.

Concomitant medication is defined as any nonstudy medication that is started accordingly:

- Before the date of first administration of INCAGN01949 and is ongoing throughout the study or ends on/after the date of first study drug administration.
- On/after the date of first administration INCAGN01949 and is ongoing or ends during the course of study drug.

A prior medication could also be classified as "both prior and concomitant medication" if the end date is on or after first dose of INCAGN01949. In the listing, it will be indicated whether a medication is prior-only, concomitant-only, or both prior and concomitant medication.

For the purposes of analysis, all medications will be considered concomitant medications unless the medications can unequivocally be defined as not concomitant.

4.2.2. Variables to Be Derived Only If Not Provided on Case Report Form

The following variables will only be calculated if not reported on the CRF.

- Subject age will be calculated as the integer part of the number of years from date of birth to the date of signing the informed consent form, using the following formula:

$$\text{Age} = \text{integer part of } (\text{date of informed consent} - \text{date of birth} + 1) / 365.25$$

5. STATISTICAL METHODOLOGY

5.1. General Methodology

Unless otherwise noted, SAS® software (SAS Institute Inc, Cary, NC; Version 9 or later) will be used for the generation of all tables, graphs, and statistical analyses. Descriptive summaries for continuous variables will include, but not be limited to, the number of observations, mean, standard deviation, median, minimum, and maximum. Descriptive summaries for categorical variables will include the number and percentage of subjects in each category.

Interim analyses are planned for this study as defined in [Section 9](#).

5.2. Treatment Groups

This is a Phase 1/2, open-label, nonrandomized, multicenter, dose-escalation study. Up to 7 doses will be tested. Data will be summarized overall and by treatment group. Treatment group is defined as the dose regimen initially assigned. Treatment cycles will begin every 14 days (\pm 3 days) but are flexible for different dose schedules based on emerging safety, PK, [REDACTED] data.

- 2 mg
- 7 mg
- 20 mg
- 70 mg
- 200 mg
- 350 mg
- 700 mg

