Additional subjects will be enrolled in a cohort to achieve the minimum of 3 evaluable subjects. Subjects who drop out for reasons other than a DLT (eg, events clearly associated with the underlying disease, disease progression, concomitant medication, or comorbidity) during the 28-day DLT observation period will be considered nonevaluable and will be replaced. Dose modifications should not be made during the DLT observation period without discussion with the medical monitor. Intrasubject dose escalation is not permitted; however, once the recommended dose has been determined, ongoing subjects in Part 1 may be permitted to escalate the dose to the recommended level with approval of the medical monitor. The cohorts and dose levels are shown in [Table 2](#).

Table 2: INCAGN01949 Dose Levels and Cohort

Cohort	Dose of INCAGN01949 ^a
-1	2 mg ^b
1 (starting dose)	7 mg
2	20 mg
3	70 mg
4	200 mg
5	350 mg
6	700 mg
7	1400 mg ^c

^a Additional dose schedules may be explored that would depend on PK, [REDACTED], and safety results.

^b Subjects who require a dose reduction below 2 mg should be discontinued from study drug.

^c Cohort 7 may be evaluated if the MTD has not been established and translational data indicate that a higher dose of INCAGN01949 may be necessary to confirm the optimal PAD.

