5.4. Treatment Interruptions and Adjustments

5.4.1. Dose Modifications

Selections and modifications to the study drug regimen are planned for dose-escalation cohorts. Dose interruptions and modifications also may occur for individual study subjects. The identification of DLTs will define the doses used in planned cohorts (see [Section 5.4.2](#)). Further, the occurrence of DLTs and other toxicities (related or unrelated to study drug) will guide decisions for treatment interruptions and discontinuation for individual subjects.

Intrasubject dose escalation is not permitted; however, once the recommended dose has been determined, ongoing subjects in Part 1 may be permitted to dose escalate to the recommended dose and schedule with approval of the medical monitor.

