5.3.3. Part 2 Full Analysis Set Population

The Part 2 FAS population includes all subjects in the FAS population enrolled in Part 2 of the study who received at least 1 dose of the MTD/PAD of INCAGN01949. Subjects tested in Part 1 (dose escalation and safety expansion) who are treated at the MTD/PAD and in Part 2, are of the same tumor type, and who meet inclusion/exclusion criteria used for the tumor type of interest in Part 2 will be combined for both safety and efficacy summary purposes.

Specific analysis populations to be used for evaluating the Simon 2-stage efficacy rules include the following subgroups:

- Part 2 FAS population subjects with adenocarcinoma of endometrium
- Part 2 FAS population subjects with melanoma
- Part 2 FAS population subjects with ovarian cancer
- Part 2 FAS population subjects with NSCLC
- Part 2 FAS population subjects with RCC

Table summaries, unless otherwise indicated, will be provided by tumor-specific cohort.

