8.2.4. Immune-Related Adverse Events

The number of subjects with irAEs and type of irAE will be listed by dose level (and by schedules) and by tumor type. Adverse event terms will be reviewed periodically without respect to treatment group by the medical monitor and clinical scientist to determine which AE terms correspond to irAEs. This periodic review may also occur after database lock. The medical monitor and clinical scientist will also review investigator reported AEs to determine if they qualify as irAEs. For example, a rash will be counted as an irAE even if the investigator did not report it as an irAE.

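### AEs that start after a Part 1 subject escalates to the recommended dose are counted under the lower starting dose, and no planned AE table separates them

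*SAP*

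**What the plan says.** **Grouping.** SAP 5.2 (Treatment Groups) fixes the rule: "Treatment group is defined as the dose regimen initially assigned". SAP 8.2.5 presents AEs by that group, and the Part 1 AE shells in SAP Appendix A (Table 3.2.1.1 onward) have one column per dose.

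**Escalation within a subject.** Protocol 4.1.1.1 forbids it with one exception. Once the recommended dose is known, "ongoing subjects in Part 1 may be permitted to escalate the dose to the recommended level with approval of the medical monitor". Protocol 5.4.1 extends this to the schedule: "ongoing subjects in Part 1 may be permitted to dose escalate to the recommended dose and schedule with approval of the medical monitor". SAP 3.1.1 repeats the provision, so the analysis plan was written with it in view.

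**AE window.** Under SAP 8.1, "table summaries will be limited to AEs occurring within 60 days of the last administration of study drug". Nothing ends or restarts the window when the dose changes.

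**Pooling with Part 2.** SAP 5.3.3 takes Part 1 subjects "who are treated at the MTD/PAD and in Part 2, are of the same tumor type" and who satisfy the Part 2 entry criteria. These "will be combined for both safety and efficacy summary purposes". The section does not mention subjects who reached that dose by escalating.

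**The concern.** The frequency, duration and severity of AEs form the primary endpoint, and Part 1 reads them by dose. A column headed with a low dose should describe what happened on that dose. If it also holds events that started on a higher dose, it can make the low dose look less well tolerated than it was, and a reader of the AE table alone cannot tell. Late safety by dose is of real interest here, because the treatment is continued for as long as the subject benefits.

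SAP 5.3.3 leaves a related question open. An escalated subject has received the higher dose, but under SAP 5.2 does not belong to that dose group. The SAP does not say which of these facts governs entry to the Part 2 analysis set.

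**Working it through.** The plan gives no figure on this point, so there is none to reproduce. The check follows one subject through the rules and then sizes the effect.

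**Tracing one subject.** Call the starting dose A and the recommended dose R, with A below R.

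1. The subject is assigned A, so the treatment group is A for the whole study (SAP 5.2).
2. After the recommended dose is set, the subject moves to R (Protocol 4.1.1.1 and 5.4.1, SAP 3.1.1).
3. A first Grade 3 event starts while the subject is receiving R. It lies inside the 60-day window of SAP 8.1.
4. SAP 8.2.5 and the shells place it in column A. No rule cuts, reassigns or flags it.
5. In the maximum-severity tables (3.2.5.1 and those like it) each subject is counted once at the highest grade. A Grade 2 event on A that recurs as Grade 3 on R is therefore shown as Grade 3 under A.

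**What other outputs show.** Table 3.1.1.1 gives average dose, and Table 3.1.2.1 gives dose by cycle with its minimum, median and maximum. A raised average or maximum could reveal that column A mixes doses. Neither table links a dose to an AE, and the Table 3.1.2.1 shell shows only Cycles 1 to 6. Listings 2.6.1 (dosing) and 2.6.2 (AEs) allow the link to be rebuilt subject by subject.

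**Size.** Inputs: SAP 3.4.1 gives a minimum of 3 and a maximum of 6 evaluable subjects per escalation cohort. If one subject in a column of n has no qualifying event in a given row before escalation and one after it, the column percentage shifts by 100 × 1/n:

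- n = 3: 100/3 = 33.3 points
- n = 6: 100/6 = 16.7 points

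These are upper values. The Part 1 analysis set counts every treated subject, so replaced subjects enlarge n. If a safety expansion cohort of 9 shares the column with 6 escalation subjects, n = 15 and the shift is 100/15 = 6.7 points. A subject who already had an event in that row before escalation shifts nothing. The Total column counts the subject once either way.

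**SAP 5.3.3 beside SAP 5.2.** The pooling condition can be read as initial assignment, which matches 5.2, or as any receipt of the dose, which would admit escalated subjects. The labels also differ: escalation goes to the recommended dose, while 5.3.3 names the MTD/PAD, and Protocol 4.1.1.2 lets the recommended dose come from expansion cohorts at or below the MTD. The text does not settle the reading.

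**The case against.** The strongest reply is that SAP 5.2 is a declared convention, not an oversight. Grouping by initial assignment is legitimate, it was stated in advance, and it avoids charging a delayed event to the wrong dose. Protocol 8.8 warns that immune-related events may appear months after treatment. This stands, and it is why the starting-dose tables should remain the main ones.

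It can also be said that the exposure tables hint at mixed dosing, that the listings permit reconstruction, that SAP 8.1 leaves room ("Additional summaries for specific subgroups may be included on an ad hoc basis"), and that Appendix A lets shells change without an amendment. All of this is true and keeps the point small. But none of it fixes a rule beforehand, so the attribution of later events would be chosen after the AEs had been seen.

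The SAP 5.3.3 gap is narrow too. Pooling needs a matching tumor type and the Part 2 entry criteria, including willingness to have biopsies, whereas pretreatment biopsy is optional in dose escalation. Few escalated subjects may qualify on any reading.

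A reader might infer that SAP 8.2.4 has the same defect, since it says "The number of subjects with irAEs and type of irAE will be listed by dose level (and by schedules) and by tumor type" without stating which dose is meant. The documents do not support that. The SAP shells use dose level and treatment group interchangeably, so with SAP 5.2 the phrase most naturally means the initial dose.

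**Conclusion.** The point holds as a minor one. If a Part 1 subject escalates, later AEs are counted under the lower starting dose in tables of the primary endpoint, and no planned AE table shows this. The shift is at most 33 points per escalated subject in a column of 3, or 17 in a column of 6. This assumes that the subject's only event in that row follows escalation. The documents give no number of escalated subjects, and it may be zero, so no probability is attached.

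Three stronger readings are tempting and should be resisted.

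- *That dose-finding is distorted.* Protocol 5.4.2 bases escalation decisions on events through Day 28, and intrasubject escalation is open only once the recommended dose is set.
- *That the later rule on the maximum number of tolerated doses is distorted.* The documents have that number determined by the sponsor with the investigators from all available safety data, and do not tie it to these tables.
- *That Part 2 results are contaminated.* SAP 5.3.3 does not say that escalated subjects are pooled. It only fails to exclude them, so no size can be given.

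Whether escalation should be permitted is a clinical matter and is not judged here.

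**What to change.** 1. Keep the AE tables by initial dose as the main Part 1 tables, and flag subjects who escalated.
2. Add one supplementary Part 1 AE summary. It ends each subject's contribution to the starting-dose column at the first infusion above the initial dose, and shows later AEs separately by initial dose and dose at onset. Footnote that delayed events may belong to the earlier dose.
3. In SAP 5.3.3, define the pooling condition by initial assignment, in line with SAP 5.2. Escalated subjects then stay out of the Part 2 analysis set for safety and efficacy alike, so both keep the same denominators.

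Cost: short statements in SAP 5.2 and 5.3.3, one derived variable (dose at AE onset) from dosing records already collected, and one table that is empty if nobody escalates. Dosing, eligibility, sample size and the efficacy grouping by initial dose do not change. The downside is that dose at onset can charge a delayed low-dose event to the higher dose, which is why the new table stays supplementary.
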